3.1 Determination of Sample Size

This is an exploratory study and no formal sample size calculation was performed.

Approximately 10 study centers worldwide are expected to participate in subject enrollment and treatment. The study is planned to enroll and treat approximately 30 subjects.

3.2 Analysis Populations

The analysis populations to be used in the analysis are defined as follows:

Intent-to-Treat Population: The intent-to-treat (ITT) population will include all subjects who are enrolled in the study.

Per-Protocol Population: The per-protocol (PP) population will include all ITT subjects who receive at least 10 total days of antifungal therapy (ibrexafungerp), who have an EoT assessment and who have no major protocol violations that would impact the assessment of efficacy.

Safety Population: The safety population will include all subjects who receive at least one dose of study medication and have at least one safety assessment post Baseline.

Pharmacokinetic (PK) Population: There will be no PK population since no PK analysis were conducted during the study.

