6.2.1 Study Participation Calculation and Extent of Exposure

The duration of study participation (days) is calculated as date of Study Completion/Termination recorded on the End of Study page – first dose date + 1. If the date of Study

Completion/Termination on the End of Study page is missing, or if a subject is lost to follow-up, the latest available visit date will be used.

The duration of study treatment (days) is calculated as last dose date – first dose date + 1.

The cumulative doses taken across the treatment period will use the exposure and missed dose log. All enrolled subjects will receive an initial oral loading dose of 750 mg of ibrexafungerp (3 tablets of 250 mg) BID during the first 2 days of treatment and then subsequent oral doses of 750 mg QD for up to 90 days. The missed dose log will be used to subtract the total number of missed doses from these total cumulative doses.

The duration of study participation, duration of study treatment, and the cumulative doses will be summarized by summary statistics. All this exposure information will be presented in a listing.

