7. EFFICACY

The primary efficacy and secondary efficacy endpoints will be performed on the ITT and PP populations. The ITT analyses will be considered primary and the PP analysis will be considered supportive of the primary analyses on the ITT population.

The primary efficacy endpoint of the study is the percentage of subjects who achieve Global Success at EOT, as determined by the DRC. Secondary efficacy endpoints include the percentage of subjects with a recurrence of the baseline fungal infection 42 days after EoT (Week 6 Follow up) as determined by the DRC, and the percentage of subjects surviving 42 and 84 days after Day 1 (first dose of study drug).

Efficacy outcomes will be based on definitions captured in Table 3. Criteria for the Investigator is outlined in Section 7.3.

Additional efficacy endpoints to be evaluated are in Section 7.3.

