7.2 Secondary Endpoints

Secondary efficacy assessment includes recurrence (after EoT) and survival.

The percentage of subjects with a recurrence of the baseline fungal infection 42 days after EoT (Week 6 Follow up) as determined by the DRC will be presented with 95% CIs for the ITT and PP populations using the same approach as for the primary endpoint. Recurrence is defined as global success at EoT but re-emergence of the baseline *Candida auris* infection during the post treatment follow-up. Re-emergence of the *Candida auris* infection is required to be with the same species and involving the same site that was initially identified at Screening/Treatment Day 1.

The percentage of subjects surviving at the defined time points will be presented for the ITT and PP populations. A Kaplan Meier plot will also be produced summarizing the survival curve over time and the median time to death. A subject without a reported death will be censored at the point of last time the subject was known to be alive. The probability of survival will be calculated at 42 and 84 days after Day 1 (first dose of study drug).

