7.3 Exploratory Endpoints

Exploratory categorical endpoints will be presented with 95% CIs for the ITT and PP populations using the same approach as for the primary endpoint.

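### Per-protocol survival runs from first dose, but entry to the per-protocol set requires being alive on Day 10, so deaths on Days 1-9 cannot appear

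*SAP*

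**What the plan says.** SAP 3.2 admits to the PP set those ITT subjects "who receive at least 10 total days of antifungal therapy (ibrexafungerp), who have an EoT assessment", provided they have no major violation affecting efficacy. Protocol 20.2 has the same rule. Both name the study drug in parentheses, so earlier IV antifungal days do not count.

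SAP 6.2.1 counts treatment inclusively: "The duration of study treatment (days) is calculated as last dose date – first dose date + 1". SAP 3 makes the first-dose date study Day 1, with no Day 0.

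On survival, SAP 7.2 states: "The percentage of subjects surviving at the defined time points will be presented for the ITT and PP populations". The clock starts at first dose: "The probability of survival will be calculated at 42 and 84 days after Day 1 (first dose of study drug"). The only risk-set rule is censoring when last known alive. SAP 7.2 adds: "A Kaplan Meier plot will also be produced summarizing the survival curve over time and the median time to death". That sentence names no population, but SAP 7 says "The primary efficacy and secondary efficacy endpoints will be performed on the ITT and PP populations", and Protocol 20.7.2 mentions Kaplan-Meier curves in the same sentence as ITT and PP.

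SAP 7 also ranks the two sets: "The ITT analyses will be considered primary and the PP analysis will be considered supportive of the primary analyses on the ITT population".

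All-cause mortality at Day 30 is an additional exploratory analysis in SAP 7.3.1 with no stated population. The lead-in at SAP 7.3 says "Exploratory categorical endpoints will be presented with 95% CIs for the ITT and PP populations", so a PP version may be intended.

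**The concern.** A minimum-exposure rule can be sensible for response at end of treatment. For survival timed from first dose it selects on the outcome, because a subject who dies in the first nine days can never accrue the exposure needed to be counted. That stretch of follow-up is immortal time.

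The study has one arm, so no concurrent PP control carries the same selection, and the PP figure alone does not show how much of it is due to the entry rule. Because the SAP calls PP supportive, a reader will naturally take agreement with ITT as reassurance. Protocol 12.1 also plans to set the results against historical standard-of-care subjects without saying which population is used. If PP survival were used, a group guaranteed alive through Day 9 could be compared with one that has no such guarantee.

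**Working it through.** The documents give no expected survival and no sample-size calculation, so there is no planned figure to reproduce. The check has a logical part, which needs no assumption, and an illustrative part, which does.

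**Logic.** Treatment days = last dose date − first dose date + 1 (SAP 6.2.1). Requiring at least 10 puts the last dose on study Day 10 or later, so a PP member must be alive on Day 10. If total days means days actually dosed, interruptions only move that date later. Twice-daily loading adds doses, not days. Hence PP deaths on Days 1-9 = 0 and PP survival over those 9 elapsed days = 100%. A simulation of 200,000 subjects with 30% Day-42 mortality confirmed this: no PP deaths on Days 1-9, and Day-42 survival of 75.5% in PP against 69.9% in ITT.

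**Size, under assumptions.** Let S be Day-42 survival, with constant hazard and no other PP exclusion. The nearest figure in the documents is roughly 30% in-hospital death in drug-resistant candidemia (SAP 1). It has no fixed time point and is not specific to *C. auris*, so a range is shown.

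- Survival to 9 elapsed days: S^(9/42)
- Share of Day-42 deaths in that period: (1 − S^(9/42)) / (1 − S)
- Expected early deaths in 30 subjects: 30 × (1 − S^(9/42))
- PP survival from the rule alone: S / S^(9/42) at Day 42 and S² / S^(9/42) at Day 84

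| | S = 80% | S = 70% | S = 60% |
|---|---|---|---|
| S^(9/42) | 0.9533 | 0.9264 | 0.8963 |
| Share of Day-42 deaths that are early | 23.3% | 24.5% | 25.9% |
| Early deaths in 30 | 1.40 | 2.21 | 3.11 |
| PP Day 42 (gain, points) | 83.9% (+3.9) | 75.6% (+5.6) | 66.9% (+6.9) |
| ITT Day 84 | 64.0% | 49.0% | 36.0% |
| PP Day 84 (gain, points) | 67.1% (+3.1) | 52.9% (+3.9) | 40.2% (+4.2) |

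**Sensitivity.**

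- Lower mortality: at S = 90%, 0.90 / 0.90^(9/42) = 92.1%, about +2 points. At S = 95%, the gain is about +1 point.
- Slower mortality: if 20%, 30% or 40% die by Day 84 rather than Day 42, PP Day-84 survival is 81.9%, 72.7% or 63.4% (+1.9, +2.7, +3.4).
- Front-loaded deaths: if half of the Day-42 deaths fall on Days 1-9, the Day-42 gains are +8.9, +12.4 and +15.0 points for S = 80%, 70% and 60%.
- No deaths on Days 1-9: the gain is 0.

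**Whole-number example.** Take 30 subjects with 9 deaths by Day 42, and Clopper-Pearson intervals. ITT is 21/30 = 70.0% (50.6-85.3%). With two early deaths removed, PP is 21/28 = 75.0% (55.1-89.3%). If PP also loses 3, 5 or 7 survivors for other reasons, it becomes 18/25 = 72.0%, 16/23 = 69.6% or 14/21 = 66.7%.

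**Day-30 mortality, only if shown for PP.** ITT is 1 − S^(30/42) = 14.7%, 22.5%, 30.6%. PP is 1 − S^(21/42) = 10.6%, 16.3%, 22.5%.

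**The case against.** The strongest reply is that little depends on this output. ITT survival is primary and shows early deaths directly. Supporting listings are planned, and with about 30 subjects early deaths can be counted by hand. The study is exploratory and descriptive, and no test or decision rule uses PP survival. The 10-day condition is disclosed in the PP definition, so a footnote might be enough. The assumed mortality may also be too high: the trial excludes hemodynamically unstable subjects and those with an Apache score above 16, and it enrols step-down patients. The net PP-ITT difference could go either way, and at this sample size any shift sits well inside the confidence interval.

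Much of this stands. The issue is confined to a supportive output, a careful reader of the ITT results can spot early deaths, the size is unknown, and low early mortality would make it small. Two points do not stand. A footnote would disclose the selection but leave an estimate timed from first dose that no early death can lower. The interval describes sampling error and does not allow for a systematic shift. The uncertain net direction also counts against the PP figure: agreement with ITT may only mean that dropped early deaths and dropped survivors cancelled.

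**Conclusion.** The concern holds. That PP survival is 100% over Days 1-9 follows from the documents' own definitions and needs no assumption. The EoT-assessment requirement may extend the selection further, by removing subjects who die on treatment after Day 10 without one.

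The effect on the Day-42 and Day-84 figures is illustrative. It is about +4 to +7 points at Day 42 and +3 to +4 at Day 84, under a constant hazard, 20-40% Day-42 mortality and no other PP exclusion. It is smaller with lower or later mortality, larger if deaths are front-loaded, and nil without early deaths. These figures isolate the entry rule and do not predict the reported PP-ITT difference.

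The PP Kaplan-Meier curve is affected in the same way if one is produced, as SAP 7 and Protocol 20.7.2 imply. PP Day-30 mortality would be too, though the SAP does not clearly call for it. The plan should be changed, but ITT survival is not at risk.

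**What to change.** In SAP 7.2, report the survival percentages and the Kaplan-Meier analysis in the ITT population only. In SAP 7.3.1, name ITT as the population for Day-30 mortality. Align Protocol 20.7.2, or record the departure from it in the SAP.

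If an exposure-restricted analysis is kept:

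- Make it a Kaplan-Meier estimate with delayed entry on the date each subject completes the 10th treatment day, not a simple percentage from first dose. Subjects whose dosing was interrupted then stay in.
- State whether treatment days are dosed days or the calendar span of SAP 6.2.1.
- Do not require an EoT assessment for it. It is then no longer the PP set and should not carry that name.
- Label it as conditional on surviving and completing 10 treatment days.

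The cost is a SAP amendment, which SAP 1 requires for changes after signature and before database lock, plus the protocol alignment or note. No new data are needed. One supportive PP survival output is dropped or relabelled.

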16.20 Adverse Event Monitoring

AEs will be collected and evaluated from the time the informed consent is signed through the EoT. After the EoT and up to the last observation in the study (Week 6 Follow-up), new AEs will be collected only if deemed related to the study drug, if they are serious adverse events (SAEs), or if they are related to a fungal infection.

See Section 18.0 for details regarding safety assessment and monitoring.

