18.0 Safety Assessments and Monitoring

18.1 Definition of an Adverse Event

An AE is any untoward medical occurrence associated with the use of a drug in humans, whether or not considered drug related. An AE can therefore be any unfavorable and unintended sign (including an abnormal laboratory finding), symptom or disease temporally associated with the use of a study drug/study intervention, whether or not related to the study drug/study intervention.

Any laboratory abnormality that is deemed to be clinically significant in the opinion of the investigator will be considered an AE and should be recorded in the eCRF, whether or not it is related to the study drug.

Stable chronic conditions that are present prior to clinical trial enrollment and do not worsen are not considered AEs and will be accounted for in the subject's medical history.

The following can be considered AEs:

- An exacerbation of a pre-existing illness
- An increase in frequency or intensity of a pre-existing episodic event or condition
- A condition detected or diagnosed after the initiation of treatment with study medication, even though it may have been present prior to the start of the study
- Continuous persistent disease or symptoms present at Baseline that worsen after signing the informed consent or following the initiation of treatment with study medication

The following are **not** considered AEs:

- Medical or surgical procedures (e.g., surgery, endoscopy, tooth extraction or transfusion); the condition that leads to the procedure is an AE
- Pre-existing disease or conditions present or detected at the start of the study that do not worsen
- Situations where an untoward medical occurrence has not occurred (e.g., hospitalizations for cosmetic surgery or elective surgery or social/convenience admissions)

• The disease being studied or signs or symptoms associated with the disease, unless more severe than expected for the subject's condition or a worsening of the disease being studied

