20.2 Analysis Populations

Intent-to-Treat (ITT) Population: The ITT Population will include all subjects who are enrolled in the study.

Per-Protocol (PP) Population: The PP Population will include all ITT subjects who receive at least 10 total days of antifungal therapy (SCY-078), who have an EoT assessment and who have no major protocol violations that would impact the assessment of efficacy.

Safety Population: The Safety Population will include all subjects who receive at least one dose of study medication and have at least one safety assessment post baseline.

PK Population: The PK Population will include all enrolled subjects who provide at least one PK sample.

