7.3.2 Clinical and Mycological Outcome

Clinical success is defined as a complete clinical response (the resolution of all clinical signs and symptoms and/or radiological abnormalities from baseline attributable to the *Candida auris* infection) or a partial clinical response (major improvement of all clinical signs and symptoms and/or radiological abnormalities from baseline attributable to the *Candida* auris infection).

Mycological success is defined as a mycological response (mycological clearance (direct and/or negative cultures [when obtainable] and/or normal serological results [when appropriate]).

8. Safety

The safety analyses will be performed on all subjects in the safety population. Analyses will be based on physical exam, vital signs, 12-lead ECGs, safety laboratory tests (hematology, blood chemistry and urinalysis), concomitant medications, AEs and treatment discontinuations. Safety analyses in general will be descriptive and will be presented in tabular format with the appropriate summary statistics.

Individual subject listings will be provided to support the tables.

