8.1 Adverse Events

All AE summaries will be restricted to treatment-emergent AEs (TEAEs) only. A TEAE is defined as any event not present before exposure to study drug or any event already present that worsens in either intensity or frequency after exposure to study drug.

For the purpose of inclusion in TEAE tables, incomplete AE start and end dates will be imputed as follows:

Missing onset dates (where UK and UNK indicate unknown or missing day and month respectively):

- UK-MMM-YYYY: If the month and year are different from the month and year of the date of first dose, assume 01-MMM-YYYY. If the month and year are the same as the month and year for the date of first dose, and the end date (after any imputation) is on or after the date of first dose, then assume the date of first dose. If the month and year are the same as the date of first dose, and the end date (after any imputation) is prior to the date of first dose, then assume the end date for the start date.
- DD-UNK-YYYY/UK-UNK-YYYY: If the year is different from the year of the date of first dose, assume 01-JAN-YYYY of the collected year. If the year is the same as the date of first dose year, and the end date (after any imputation) is on or after the date of first dose, then assume the date of first dose. If the year is the same as the date of first dose, and the end date (after any imputation) is prior to the date of first dose, then assume the end date.

Missing end dates (where UK and UNK indicate unknown or missing day and month respectively):

- UK-MMM-YYYY: Assume the last day of the month;
- DD-UNK-YYYY/UK-UNK-YYYY: Assume 31-DEC-YYYY.

All adverse events will be classified by SOC and PT according to the Medical Dictionary for Regulatory Activities (MedDRA, March 2023 Version). An overview summary of the number and percentage of subjects with any TEAE, serious TEAE, treatment-related TEAE, treatment-related serious TEAE, TEAE leading to study treatment discontinuation, TEAE leading to study discontinuation, and AE leading to death will be provided.

All AEs will be presented in a listing.

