8.1.5 Death

All subjects who have an AE with an outcome of "Death Related to Adverse Event" will be presented in a listing.

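### The safety population rule and the only death listing in SAP section 8 can leave out deaths that the survival analysis counts, and no reconciliation is planned

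*SAP*

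**What the plan says.** **Who is in the safety set.** SAP 3.2: "The safety population will include all subjects who receive at least one dose of study medication and have at least one safety assessment post Baseline". Protocol 20.2 sets the same two conditions: subjects must "receive at least one dose of study medication and have at least one safety assessment post baseline". Neither document says what counts as a safety assessment. The opening of SAP section 8 says "The safety analyses will be performed on all subjects in the safety population" and includes in the safety data "concomitant medications, AEs and treatment discontinuations".

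**Where section 8 reports deaths.** There are two places, both built on AE records. The overview table in SAP 8.1 ends with "TEAE leading to study discontinuation, and AE leading to death will be provided". SAP 8.1.5 says "All subjects who have an AE with an outcome of 'Death Related to Adverse Event' will be presented in a listing". Section 8 specifies no all-cause death table or listing.

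**When AE collection stops.** Protocol 16.20 ends it at the Week 6 Follow-up, 42 days after end of treatment (EoT). After EoT only drug-related, serious or fungal-infection-related new events are taken. The Day 42 and Day 84 survival contacts (protocol 20.7.1.2) record whether the subject is alive and, for a death, its relationship to the fungal infection.

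**Where else deaths are counted.** SAP 7.2 gives survival at 42 and 84 days in ITT and PP with Kaplan-Meier. SAP 7.3.1 adds Day 30 all-cause mortality and the DRC's opinion on the cause of any death. SAP 4.1 has death as a discontinuation reason, with a listing.

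**The concern.** Both rules select on what happens after dosing. The second condition for the safety set can only remove subjects who were dosed and then not assessed, and early death is one way for that to happen. The death listing depends on how and when a death was recorded, not on whether it occurred.

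At stake is the consistency of the report. The survival analysis includes all enrolled subjects and every known death. The safety section may rest on fewer subjects and show fewer deaths, and a reader of the CSR would have no planned output that explains the difference.

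**Working it through.** **Inputs.** Treatment up to 90 days (protocol 14.1); Week 6 Follow-up at EoT + 42 days; survival contacts at Days 42 and 84; visit windows of ±2 days; planned N about 30 with no formal calculation (SAP 3.1); at least 10 days of study drug for PP (SAP 3.2).

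**Check of the plan's own figure.** 90 + 42 = 132 days, which matches protocol 12.3. There are no inputs from which to reproduce N = 30.

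**Late deaths.** Time between the close of AE collection and the Day 84 contact = 84 − (EoT day + 42) = 42 − EoT day.

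| EoT day | Week 6 Follow-up | Gap to Day 84 |
|---|---|---|
| 10 | Day 52 | 32 days |
| 14 | Day 56 | 28 days |
| 28 | Day 70 | 14 days |
| 41 | Day 83 | 1 day |
| 42 | Day 84 | 0 |
| 60 | Day 102 | none |

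The ±2-day windows on the follow-up visit and on the contact can together move a gap by up to 4 days. A death in the gap is found at a contact that records vital status and relationship to the infection, after routine AE collection has ended. SAP 7.2 counts it; SAP 8.1.5 has no AE record to list. Short courses are foreseeable, because duration is left to the investigator and 10 days is enough for PP.

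**Early deaths.** From the schedule of visits (protocol Table 1):
- Day 2: visit for the PK subset only.
- Days 3 to 5: first scheduled post-dose visit for everyone else, with targeted examination and AE monitoring but no safety laboratory tests.
- Days 7 to 10: first scheduled post-baseline laboratory tests.
- EoT: next scheduled vital signs and ECG. The general physical examination is at EoT and at Week 6 Follow-up.

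A dosed subject who dies before Days 3 to 5 may have no scheduled assessment. The documents give no rate for this. If the chance per subject is q (an assumption), the chance of at least one among 30 is 1 − (1 − q)^30: 26% for q = 1%, 60% for 3%, 79% for 5%, 96% for 10%. The expected number, 30q, is 0.3, 0.9, 1.5 and 3. Actual exclusion also requires that no AE record is accepted as an assessment.

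**What one exclusion does.** The AE percentages use the safety population as denominator (SAP 8.1.1). If 9 of 30 subjects had some event (an assumed count) and one of the 9 were excluded, 9/30 = 30.0% would become 8/29 = 27.6%.

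**Deaths recorded only under another label.** The progressive-disease category in SAP 7.1 includes deterioration resulting in death. SAP 4.1 lists death and progressive disease as reasons distinct from adverse event. A site could complete either without a fatal AE, and 8.1.5 contains no cross-check.

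**The case against.** The case on the other side is substantial.

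- **Deaths from the infection.** A reader might infer that a candidiasis death generates no AE, because protocol 18.1 exempts "The disease being studied or signs or symptoms associated with the disease, unless more severe than expected for the subject's condition". That sentence goes on to except worsening of the studied disease as well. A fatal infection has normally worsened, so it is an AE, and with a fatal outcome an SAE under 18.2. What remains is a risk of inconsistent recording.
- **Drug-attributable deaths.** A reader might also infer that these are the ones lost. The documents do not support that. Such a death is a related, serious AE, the disease exemption cannot apply, SAP 8.1 lists all AEs, and 8.1.5 is worded for all subjects with a fatal AE.
- **Early deaths.** AE monitoring is scheduled at every visit and AEs are collected from consent. If an AE or discontinuation record counts as an assessment, the subject stays in. That reading is reasonable, but the plan does not state it.
- **Effect on mortality.** One might say each omitted death costs 1/30 = 3.3 points of mortality. No planned all-cause mortality estimate uses the safety population. Survival is analysed in ITT and PP, and ITT is all enrolled subjects, so the safety-set rule removes no death from the ITT result.
- **Late deaths.** They fall more than six weeks after EoT, and protocol 18.11 follows existing AEs to an outcome, so an event that began in time and later proved fatal could be listed. Protocol 18.9 runs collection to the last observation without naming the visit, which might be read as Day 84; but 16.20 names Week 6 Follow-up, and 12.1 puts the final safety assessment there. A new fatal event in the gap is still missed.

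Disposition may not close the late gap either. A subject who finished Week 6 Follow-up may already be recorded as having completed (my inference).

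**Conclusion.** The point holds as a matter of completeness and consistency within the report. Two written rules let the safety section omit subjects or deaths: an undefined second condition for the safety set, and a death listing tied to AE outcome. The late-death gap is certain in principle for any EoT before about Day 42. The early-death exclusion depends on how safety assessment is read. Deaths recorded only as progressive disease or as a disposition reason are a recording risk.

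It would be wrong to conclude that deaths disappear from the study. Early deaths reach Day 30 mortality, those up to Day 84 reach the ITT survival analysis, and the DRC reviews causality of any reported death. What is missing is an all-cause death listing in section 8 and a reconciliation with these outputs.

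The number affected is unknown. It is probably small: N is about 30, and hemodynamically unstable subjects and those with an Apache score above 16 are excluded (protocol 13.2), which should make very early death less common. This is a low-cost improvement; the primary endpoint is untouched.

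**What to change.** 1. In SAP 3.2, define the safety population as all subjects who receive at least one dose. State in the SAP that this departs from protocol 20.2, and why.
2. In SAP 8.1.5, replace the AE-outcome rule with a listing of all deaths from any source: AE form, survival contact or end-of-study page. Show study day, days since last dose, recorded relationship to the fungal infection, and DRC causality.
3. Reconcile that listing with the survival and disposition data before database lock, and explain any difference in the CSR.

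The cost is a few SAP sentences, one revised listing and a documented difference between protocol and SAP. No new data are needed: the survival contacts, disposition records and DRC review already supply the content.
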